5.3. REMOVAL OF SUBJECTS FROM STUDY TREATMENT AND/OR STUDY AS A WHOLE

Subjects can be taken off the study treatment and/or study as a whole at any time at their own request, or they may be withdrawn at the discretion of the investigator for safety, behavioral or administrative reasons. In the case that a subject is removed from the study due to safety reasons, the FDA and other global regulatory authority will be notified. The reason(s) for discontinuation must be clearly documented on the appropriate eCRF and may include:

- Subject voluntarily withdraws from treatment (follow-up permitted)
- Subject withdraws consent (no follow-up permitted)
- Subject is unable to comply with protocol requirements

CONFIDENTIAL Page 54 of 101

- Subject experiences unacceptable toxicity
- Treating physician determines that continuation on the study would not be in the subject's best interest
- Subject becomes pregnant
- Subject becomes lost to follow-up (LTF)
- Subject will be withdrawn from the study if 2 consecutive doses of study drug are missed
- Subject manifesting Grade 4 or Grade 3 toxicity attributable to the Leronlimab (PRO 140)

If a subject fails to return for the scheduled study visit or is discontinued from the study, an attempt will be made to determine the reason(s). If the subject is unreachable by telephone, a registered letter will be sent to the subject requesting that he/she contact the clinic.

All patients with an ongoing SAE or AE attributable (definitely, probably, or possibly related) to the study treatment at the Post-Study (Follow-up) Visit (scheduled or premature) must be followed until the event is resolved (with or without sequelae) or deemed stable.

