5.4. DATA COLLECTED FROM WITHDRAWN SUBJECTS

Every attempt should be made to collect follow-up information. The reason for withdrawal from the study will be recorded in the source documents and on the appropriate page of the CRF.

Before a subject is identified as lost-to-follow up, the site should make all reasonable efforts to contact the subject. These attempts must be documented and should include at a minimum one phone call and one certified letter.

[figure not shown]
In the event that a subject is withdrawn from the study at any time due to an adverse event or SAE, the procedures stated in Section 9 (Safety) must be followed.

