8.9.3. Missing Data

Every effort will be made to obtain required data at each scheduled evaluation from all subjects who have been randomized to minimize missing data. However, in the event when there is missing data the following imputation methods will be used.

For efficacy evaluations, multiple imputation methods will be used to handle missing data. This imputation method is a robust method to impute missing measurements. The imputation will be carried out in SAS version 9.4 or later using PROC MI. Each imputation model will include the stratification factor as a covariate in the model. The details of multiple imputation will be included in the statistical analysis plan.

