11.4.1. Major Protocol Deviation or Violation

A major protocol deviation or violation is a deviation from the IRB approved protocol that may affect the subject's rights, safety, or well being and/or the completeness, accuracy and reliability of the study data. Examples of this include:

- Failure to obtain informed consent prior to initiation of study-related procedures
- A research subject does not meet the protocol's eligibility criteria but was enrolled without prior approval from the sponsor.
- A research subject received the wrong treatment or incorrect dose.
- A research subject met withdrawal criteria during the study but was not withdrawn.
- A research subject received a prohibited concomitant medication.
- Failure to treat research subjects per protocol procedures that specifically relate to primary efficacy outcomes.
- Changing the protocol without prior sponsor and IRB approval.
- Multiple minor violations of the same nature after multiple warnings.

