6. ANALYSIS POPULATIONS

6.1 Modified Intent-to-Treat Population

The **Modified Intent-to-Treat (mITT) population** is defined as the set of subjects who have received at least one dose of study treatment (leronlimab or placebo). This population will be used as

the primary analysis population for analysis of the primary and secondary efficacy endpoints...

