6.2 PP Population

The **Per Protocol** (**PP**) **population** is defined as the set of subjects who meet the mITT Population requirements and are not associated with any major protocol violations. This population will be identified before the database lock. This population will be used as the supportive analysis population for analysis of the primary and secondary efficacy endpoints.

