8.1.2 Protocol Deviations

Protocol deviations will be identified and classified as minor or major before un-blinding.

Protocol deviations for all randomized subjects will be listed as by-subject listing and major deviations will be summarized descriptively according to the following categories:

- Did not meet Inclusion/Exclusion criteria but entered into study
- Developed withdrawal criteria during the study but not withdrawn
- Received excluded concomitant medication
- Study treatment dosing deviation

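### Two consecutive missed doses lead to withdrawal from the study, not only from treatment, and no text then requires the diary or PROMIS through Day 56

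*Combined protocol and SAP*

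**What the plan says.** Protocol 5.3 covers removal from study treatment and removal from the study as a whole. Its list of reasons for discontinuation includes "Subject will be withdrawn from the study if 2 consecutive doses of study drug are missed". The lead-in says that the documented reasons may include those listed. Another item reads "Subject voluntarily withdraws from treatment (follow-up permitted"), and withdrawal of consent is the one item that rules follow-up out.

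Protocol 11.4.1 gives as an example of a major deviation: "A research subject met withdrawal criteria during the study but was not withdrawn". SAP 8.1.2 has a matching category for summarising major deviations: "Developed withdrawal criteria during the study but not withdrawn".

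The mITT set (SAP 6.1) consists of subjects who "received at least one dose of study treatment (leronlimab or placebo"). Later withdrawal does not remove anyone from it. The PP set (SAP 6.2) is the mITT subjects who "are not associated with any major protocol violations".

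On data after withdrawal, protocol 5.4 says "Every attempt should be made to collect follow-up information". Protocol 8.9.3 says "Every effort will be made to obtain required data at each scheduled evaluation from all subjects who have been randomized", and SAP 7.3 repeats this. The two then diverge: the protocol prescribes multiple imputation for efficacy, and the SAP says that missing data are not imputed.

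The diary is scheduled for the treatment phase (Table 4-2, note 7) or treatment period (7.15). The last treatment-phase visit counts as the EOT visit and includes all three PROMIS forms (4.2.4). The follow-up visit V18 has neither diary nor PROMIS (4.3.1).

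**The concern.** The primary endpoint, as defined in protocol 8.2.1 and SAP 3.1, and three secondary endpoints (symptom duration, symptom-free days, worsening) are built from diary scores through Day 56. Most diary items ask about the worst severity over the last 24 hours, so a day not recorded cannot be recovered later. The PROMIS endpoints are read at Days 28 and 56.

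A site that follows 5.3 literally may end collection early for a subject whom the primary analysis still counts. Missing doses is an event after randomization and may be related to treatment. Tables 6-3 and 6-4 have doses withheld for a Grade 3 injection-site reaction and for other attributable Grade 2 toxicity until resolution. With weekly dosing, slow resolution could produce two undosed visits in a row. The documents do not say whether a withheld dose counts as missed.

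**Working it through.** The plan gives no figure to reproduce here. The sample size of 50 rests on clinical judgment, and no missed-dose or dropout rate is stated. Two checks are possible: what the texts require, and how much data the schedule puts at risk.

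**Does any text require the diary or PROMIS to Day 56 after this withdrawal?**

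- Protocol 5.4 applies to withdrawn subjects but names no instrument, time point or end date.
- Protocol 8.9.3 and SAP 7.3 cover all randomized subjects at each scheduled evaluation. They state a general aim and give no procedure for a subject who has left the study.
- The item that permits follow-up in 5.3 concerns voluntary withdrawal from treatment. It allows follow-up without requiring it, and names neither diary nor PROMIS.
- An early EOT visit (4.2.4) could give one last PROMIS score, but not the Day 56 score or the remaining diary days.
- Section 5.3 allows for a premature follow-up visit, but V18 contains neither instrument.
- Note 7 of Table 4-2 and section 7.15 could be read as covering 56 calendar days. They do not say that the diary continues once dosing stops.

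None of these requires it.

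**What the schedule puts at risk.** Inputs from Table 4-2: doses on nominal Days 0, 7, 14, 21, 28, 35, 42 and 49; diary through Day 56; eight post-baseline PROMIS visits (V4, V6, V8, V10, V12, V14, V16, V17). For a subject who received the first dose, the rule is met on the day of the second consecutive missed dose.

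Diary days at risk = 56 − removal day; share = days at risk / 56.

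| Missed doses (days) | Removal day | Diary days at risk | Share of 56 | PROMIS visits left of 8 |
|---|---|---|---|---|
| 7, 14 | 14 | 42 | 75% | 6 |
| 14, 21 | 21 | 35 | 62.5% | 5 |
| 21, 28 | 28 | 28 | 50% | 4 |
| 28, 35 | 35 | 21 | 37.5% | 3 |
| 35, 42 | 42 | 14 | 25% | 2 |
| 42, 49 | 49 | 7 | 12.5% | 1 |

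The Day 56 PROMIS scores are at risk in all six rows. The Day 28 scores are at risk for removal on Day 14 or 21, and for removal on Day 28 if that visit is not attended.

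**Scale per subject.** With 50 subjects randomized 1:1 there are 25 per arm. If a subject's endpoint is left missing, 1/25 = 4% of the arm drops out of that analysis. If instead unrecorded days were counted as non-event days, one subject would change the arm's mean day count by at most 42/25 = 1.68 days (removal on Day 14) or 7/25 = 0.28 days (removal on Day 49), and by as little as 0. The documents do not state that convention. The planned test of the day-count endpoints is non-parametric or on ranks (SAP 8.2.2.1), so these shifts would describe summary means only.

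**The case against.** The strongest reply is that the protocol already expects data after withdrawal. Section 5.4 is about withdrawn subjects, and 5.3 bars follow-up only when consent is withdrawn. A reader might infer that a site which goes on collecting the diary breaks the protocol, or that 5.4 contradicts the order to withdraw. The documents do not support either inference. The deviation in 11.4.1 and SAP 8.1.2 is failing to withdraw. A site can withdraw the subject and still pursue data under 5.4, which governs what happens next.

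The lead-in to the list in 5.3 also softens the item, because it introduces reasons that may be documented, and the list mixes both levels of removal. Attributable Grade 3 toxicity appears there too, while Table 6-4 only stops treatment for it. This stands as a qualification, but the missed-dose item itself says the subject will be withdrawn, and from the study.

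A reader might also infer that this rule is what costs the subject a place in the PP set. That does not follow. SAP 8.1.2 lists dosing deviations among its categories for major deviations, so a subject who missed two doses could leave the PP set on that ground anyway.

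Finally, a subject who misses two clinic doses may be disengaging, and some of the loss may occur under any rule. That is fair, and it limits what the change can recover. What remains is that the plan states an aim and attaches no required assessment to it.

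**Conclusion.** The point holds as a gap between an explicit withdrawal rule and a best-effort aim. Two consecutive missed doses lead to withdrawal from the study, the subject remains in mITT, and nothing requires the diary or PROMIS through Day 56. Each such subject can lose 7 to 42 of 56 diary days and the Day 56 PROMIS scores. These figures assume the nominal schedule, a first dose received, and collection ending on the removal day.

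A reader might go on to infer a bias of known size or direction. The documents do not support that. They give no missed-dose rate, no reason to expect imbalance in either direction, and no rule for counting unrecorded days. Their missing-data rules also disagree: under SAP 7.3 the lost values are not imputed, and under protocol 8.9.3 they would be multiply imputed. The loss per subject is certain enough to be worth preventing in a trial with 25 per arm; its effect on the treatment comparison cannot be estimated. This is a cheap improvement to the design, and it does not show that the trial's result would be wrong.

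**What to change.** In protocol 5.3, make two consecutive missed doses a reason to stop study treatment only. In 5.3 and 5.4, state that after any early treatment discontinuation, unless consent is withdrawn, the daily diary and PROMIS continue as scheduled through V17 (Day 56), and hospitalization and adverse-event assessments through V18. Align Table 4-2 note 7 and section 7.15 so that the diary runs to Day 56 whether or not dosing continues. As a minor clarification, say whether doses withheld under Tables 6-3 and 6-4 count as missed.

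The cost is a protocol amendment with IRB approval and possibly a revised consent form (protocol 11.3), continued visits by undosed subjects, and some off-treatment data in the mITT analysis. No new assessment is needed, because all of them are already in the schedule.

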5.4. DATA COLLECTED FROM WITHDRAWN SUBJECTS

Every attempt should be made to collect follow-up information. The reason for withdrawal from the study will be recorded in the source documents and on the appropriate page of the CRF.

Before a subject is identified as lost-to-follow up, the site should make all reasonable efforts to contact the subject. These attempts must be documented and should include at a minimum one phone call and one certified letter.

[figure not shown]
In the event that a subject is withdrawn from the study at any time due to an adverse event or SAE, the procedures stated in Section 9 (Safety) must be followed.

5.5. SCREEN FAILURES

A subject who signed a consent form, but did not meet the inclusion/exclusion criteria is classified as a screen failure. Subject number, demographics and reason for screen failure will be recorded.

In the event that a subject initially fails to meet inclusion/exclusion criteria and is later reconsidered for participation, the subject will be re-consented and assigned a new screening number at the time of re-screening. Subjects who fail their first screening attempt may be re-screened again (i.e., up to two screenings) and may be enrolled if they are found to meet all inclusion and no exclusion criteria at the subsequent screening visit.

CONFIDENTIAL Page 55 of 101

6. STUDY TREATMENT

Leronlimab (PRO 140) or placebo will be administered subcutaneously (SC) at a weekly as follows:

Table 6-1: Treatment Administration Summary

Study Drug	Dose	Route	Schedule
Leronlimab (PRO 140)	$700~\mathrm{mg}$	SC	Weekly (8 doses)
Placebo	0 mg	SC	Weekly (8doses)

6.1. LERONLIMAB (PRO 140)

Leronlimab (PRO 140) is a humanized IgG4,κ monoclonal antibody (mAb) to the chemokine receptor CCR5. Leronlimab (PRO 140) is provided at a concentration of 175 mg/mL and is intended for SC route of administration.

Leronlimab (PRO 140) kit will contain two vials. Each vial of the Leronlimab (PRO 140) product contains ~2.4 mL antibody at 175mg/mL in a buffer containing 5 mM L-histidine, 15.0 mM glycine, 95 mM sodium chloride, 0.3% (w/v) sorbitol, 0.005% (w/v) polysorbate 20 (Tween 20[®]), and sterile water for injection, at pH of 5.5. For subjects assigned to Leronlimab (PRO 140) arm, one kit will be assigned per treatment visit.

Note: 2 mL will be drawn from 2.4 mL solution filled vial. Remaining 0.4 mL medication will be discarded appropriately from each vial.

Isotonic 0.9% Sodium Chloride Injection, USP will be used as Placebo.

A dose of 700 mg of Leronlimab (PRO 140) (175 mg/mL) or placebo will be delivered as two injections of 2 mL each and administered subcutaneously on opposite sides of the abdomen.

Table 6-2: Investigational Product - Leronlimab (PRO 140)

IP Dosage	Dosage Form	IP concentration	Dosing Frequency and Amount	Route of Administration
PRO 140 700 mg	Parenteral solution	175 mg/mL	2 injections of PRO 140 (2 mL/inj.) per week on opposite sides of abdomen for eight weeks	SC injection
Placebo	Parenteral solution	0 mg/mL	2 injections of placebo (2 X 2 mL/inj.) per week on opposite sides of abdomen for eight weeks	SC injection

Note: Patients with low body fat percentages may find subcutaneous injections uncomfortable. In such cases, leronlimab (PRO 140) 700 mg can be injected as four 175mg/ml injections and/or subcutaneous injections can be placed at different areas other than abdomen as per discretion of the Investigator.

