1.4.2.3. PRO 140 1103 Study

In PRO 140-1103, administration of PRO 140 at 350 mg using Autoject® 2 appeared well tolerated. Manual injections, on the other hand, were associated with a greater number of AEs. There did not appear, however, to be any substantial difference in subject perception of pain or discomfort related to site of drug administration. No anti-PRO 140 antibodies were detected in any subjects in this study. There was a tendency of higher exposure associated with SC administration of PRO 140 at 350 mg in the abdomen and the thigh. A higher number of AEs were associated with injections in the arm. Based on these observations, thigh and abdominal administration of PRO 140 were preferred over arm injection.

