1.4.2.19. CD12_COVID-19

CD12_COVID-19 (two-arm, randomized, double blind, placebo controlled, adaptive design) seeks to evaluate the safety and efficacy of leronlimab (PRO 140) in patients with severe or critical COVID-19.

This clinical study is currently ongoing.

Table 1-1: List of Completed Clinical Studies with Leronlimab (PRO 140)

Table 1-1. Elst of Completed Chinear Studies with Lefonthinab (1 No 140)							
Protocol Number	Phase	No. of Subjects (Planned/ Analyzed)	Doses	Subject Population	Comments		
PRO 140 1101	1	20/20	Single 0.1, 0.5, 2.0, or 5.0 mg/kg	Healthy	Generally well tolerated; non-immunogenic; dose-dependent coating of CCR5; significant coating of CCR5 over placebo at 0.5, 2, and 5 mg/kg		
PRO 140 1102	1	20/20	Either two or three doses totaling 200 or 350 mg respectively	Healthy	Generally well tolerated; drug derived from CHO cells well tolerated also; SC administration by Autoject® 2 better tolerated than manual injection		
PRO 140 1103	1	15/14	Two doses, each of 350 mg	Healthy	More AEs associated with arm injection; trend of lower exposure in arm injections; thigh and abdominal administration preferred		
PRO 140 1302	1b	40/39	Single 0.5, 2.0, or 5.0 mg/kg	HIV-1 positive	Generally well tolerated; antiviral suppression maintained for approx. 10 days with higher doses; favorable tolerability and potent, dose- dependent antiviral activity provide proof-of- concept		
PRO 140 2301	2a	30/31	Single 5.0 or 10.0 mg/kg	HIV-1 positive	Generally well tolerated with no dose-limiting toxicities; potent antiviral suppression maintained for approx. 20 days when administered IV at 5 or 10 mg/kg. No dose-limiting toxicities at 10 mg/kg.		
PRO 140 2101	2a	40/44	Three doses of 162 or 324 mg each	HIV-1 positive	Generally well tolerated, no drug-related SAEs or dose-limiting toxicity; antiviral activity was statistically significant; two-fold exposure at higher dose; single dose demonstrated favorable tolerability, and potent, long-acting, dose-dependent antiviral activity.		

CONFIDENTIAL Page 32 of 101

Protocol Number	Phase	No. of Subjects (Planned/ Analyzed)	Doses	Subject Population	Comments	
PRO 140 CD01	2b	43/43	350 mg SC weekly dose for 12 weeks of monotherapy (total treatment duration 14 weeks)	HIV-1 positive	Generally well tolerated, no drug-related SAEs or dose-limiting toxicity; Open-label administration of PRO 140 demonstrated favorable tolerability, and potent, long-acting, antiviral activity.	

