6.1.3. Leronlimab (PRO 140) - Administration

Guidelines for dose preparation can be found in the pharmacy manual.

Leronlimab (PRO 140) or placebo will be provided to the administering personnel in single-use syringes prepared from vials of study drug stored at 2-8°C at the site pharmacy prior to use. Syringes will be prepared by an unblinded pharmacist or designated site staff. Each of two syringes is filled to deliver 2 mL of study drug.

Equivalent volumes of PRO 140 will be administered subcutaneously on opposite sides of the abdomen.

A 20-guage needle should be used to remove PRO 140 from vial and a 25-guage needle is used for administration to subjects.

Note: After the leronlimab solution is drawn into the syringe, it can be stored at room temperature (20°C to 25°C, 68°F to 77°F) for up to 2 hours, or refrigerated (2°C to 8°C, 36°F to 46°F) for up to 4 hours.

IP should be administered slowly over 15 seconds per mL.

Following each SC delivery of drug, careful examination will be made to assess the appearance of any study drug Injection Site Reactions (ISRs) as per CTCAE v5.0.

Leronlimab (PRO 140) will be administered as SC injection by a qualified medical professional at the study clinic.

Note: It is preferred that the same injection site be used throughout the study. At the same time, it is not recommended to inject the study drug into areas where skin shows signs of a previous injection site reaction. It is advised to change the injection site if any previous injection site reaction remains unresolved.

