8.6. BLINDING

All subjects, Investigators and their staff (except unblinded pharmacist or designated site staff), and all Sponsor/CRO personnel involved in the management of the study will be blinded to treatment assignments.

The Amarex Information Technology department will be unblinded to treatment. As noted above, the Amarex Technology department is not otherwise involved with the study.

Treatment unblinding for the study will occur after all clinical data have been received, data inconsistencies have been resolved, and the database is locked, except for safety reasons on a case-by-case basis (i.e., emergency unblinding).

The process for emergency unblinding will be outlined in detail in the Randomization Plan. In addition, any subject that is unblinded for any reason will be identified and discussed in the final clinical study report.

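### The four-injection option for low-body-fat patients is worded for leronlimab only; followed literally, the injection count could reveal the treatment arm

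*Combined protocol and SAP*

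**What the plan says.** Protocol 6.1 sets one presentation for both arms: "A dose of 700 mg of Leronlimab (PRO 140) (175 mg/mL) or placebo will be delivered as two injections of 2 mL each", on opposite sides of the abdomen. Table 6-2 repeats this for placebo: "2 injections of placebo (2 X 2 mL/inj.) per week on opposite sides of abdomen for eight weeks". The synopsis table, Table 4-1 and SAP Table 2-2 also show placebo only as two 2 mL injections.

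The note under Table 6-2 then makes an exception for patients with low body fat: "leronlimab (PRO 140) 700 mg can be injected as four 175mg/ml injections and/or subcutaneous injections can be placed at different areas other than abdomen". The choice is left to the investigator.

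Section 6.1.3 has an unblinded pharmacist or designated site staff prepare the syringes and describes one preparation: "Each of two syringes is filled to deliver 2 mL of study drug". Section 8.6 lists as blinded "All subjects, Investigators and their staff (except unblinded pharmacist or designated site staff"), together with the sponsor and CRO personnel who manage the study.

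On injection site, the summary of study 1103 in 1.4.2.3 states: "A higher number of AEs were associated with injections in the arm". It reports a tendency to higher exposure in abdomen and thigh and a preference for those two sites. The study's row in Table 1-1 reports a "trend of lower exposure in arm injections".

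SAP 8.1.5 presents all study drug administration data and summarises the total number of injections received.

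**The concern.** The four-injection clause names leronlimab and its concentration, and no clause gives placebo the same option. The person who asks for the option is blinded; the person who fills the syringes is not. If the preparer reads the note as written, the same request produces different syringe counts in the two arms, and the administering staff see the count at each visit where the option is used, up to eight times.

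The primary endpoint is the subject's own daily symptom score (protocol 8.2.1 and Appendix 1). Of the eight secondary endpoints in 8.2.2, six are self-rated: symptom duration, symptom-free days, progression and three PROMIS scores. The other two concern hospitalization. Ratings of this kind are open to bias if the arm becomes known, and with about 25 subjects per arm a few such subjects carry weight.

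Two smaller matters sit in the same note. It does not fit the two-syringe preparation text, and its open wording on injection areas does not take up what the protocol itself reports about the arm as a site.

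**Working it through.** **1. The plan's own dose.** Inputs from 6.1: 2 injections, 2 mL each, 175 mg/mL. 2 × 2 × 175 = 700 mg, as stated.

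**2. The note against 6.1.3.** The note gives a total (700 mg), a count (four) and a concentration (175 mg/mL), but no volume. Four equal injections making up that total imply 700 / (4 × 175) = 1 mL each. Section 6.1.3 describes only two syringes of 2 mL. The two passages therefore do not describe the same preparation and must be reconciled. The 1 mL figure is only what the note's own numbers imply; it is not a recommendation.

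**3. What the count reveals.** Suppose the investigator requests the option without knowing the arm.

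| Reading of the note | Leronlimab subject | Placebo subject | P(leronlimab given four injections) |
|---|---|---|---|
| Literal: leronlimab only | four syringes | two syringes | 1.0 |
| Same option in both arms, used equally often | four syringes | four syringes | 0.5 (1:1 allocation) |

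On the literal reading the disclosure runs both ways: a request answered with two syringes points to placebo.

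**4. How many subjects.** Inputs: 50 subjects randomized 1:1 (protocol 8.3), so 25 per arm. The share f who would use the option is not in the documents and is assumed here. Expected leronlimab subjects affected = 25f; chance of at least one = 1 − (1 − f)^25.

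| Assumed f | Expected of 25 | Chance of at least one |
|---|---|---|
| 2% | 0.5 | 0.40 |
| 5% | 1.25 | 0.72 |
| 10% | 2.5 | 0.93 |
| 20% | 5.0 | >0.99 |

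If the option is requested equally often for placebo subjects, the same expected number of unmet requests arises in that arm.

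**5. Injection totals.** Eight doses give 8 × 2 = 16 injections by the standard route and 8 × 4 = 32 if the option is used every time. The SAP 8.1.5 summary would therefore show different totals for the same eight doses.

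**The case against.** The strongest reply is that this is a dropped *or placebo*. The protocol uses the drug name loosely elsewhere: 4.2.1 words the post-dose checks for all subjects as following the first leronlimab dose, and 6.1.3 speaks of equal volumes of PRO 140. A blinded investigator cannot restrict the option to one arm, and no text tells the preparer to refuse it for placebo. The pharmacy manual, which is not among the documents, may settle the matter. This stands as a plausible account of what was meant. It does not make the text safe: the dosing sentence just before Table 6-2 does name placebo, and the note specifies 175 mg/mL where the table lists placebo at 0 mg/mL, so a preparer could reasonably take the note literally.

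Some stronger readings are tempting, but the documents do not support them:

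- *A change of site also reveals the arm.* The site clause names no product, in a note about patients generally.
- *Subjects are certain to be unblinded.* A subject sees only their own injections and learns the arm only by knowing that placebo is not split. Nothing says that subjects are told this. Staff who know the protocol are the more direct route.
- *Four syringes at the 2 mL fill would deliver 4 × 2 × 175 = 1400 mg.* The note fixes the total at 700 mg, and 6.1 assigns one two-vial kit per visit and draws 2 mL from each vial: 4 mL, or 700 mg.
- *Use of the option would go untracked.* SAP 8.1.5 presents all administration data and counts injections, and protocol 6.1.2 records the amount dispensed. Only the injection site has no stated recording.
- *Exposure would fall by a known amount.* Study 1103 analysed 14 subjects at 350 mg and is reported only as a tendency or trend, without figures. The open wording also admits the thigh, which that study preferred, and 6.1.3 prefers the same site throughout.

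**Conclusion.** The point holds for the four-injection clause. As written it covers leronlimab only, and literal use by the unblinded preparer would let the syringe count show the arm to site staff, and to any subject who knows the rule. This rests on the literal reading and on the option being used at all. Its size cannot be computed from the documents; the range of 0.5 to 5 of 25 leronlimab subjects comes entirely from the assumed 2% to 20% use. Any resulting bias in the self-rated endpoints cannot be quantified either.

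The mismatch with 6.1.3 is a textual conflict to reconcile, not a predicted dosing error. The study 1103 evidence supports reconciling the site wording with the protocol's own summary and nothing stronger. The change is worth making because the protection to the blind is specific and the cost is small.

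**What to change.** 1. Reword the note under Table 6-2 so that any change in the number or site of injections applies identically to study treatment (leronlimab or placebo), with matched presentation in both arms.
2. Reconcile the note with the two-syringe text in 6.1.3, so that the stated 700 mg total and the preparation instructions agree. Carry the same wording into the pharmacy manual.
3. Reconcile the open wording on injection areas with the study 1103 summary in 1.4.2.3 and Table 1-1. The sponsor decides.
4. Record the injection site at each dose, alongside the injection number already summarised under SAP 8.1.5.

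No volume or site is proposed here. The cost is a sentence or two in 6.1, a matching line in 6.1.3 and the pharmacy manual, and one recorded item per dose. The placebo is saline and can be split to match.
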